6.1 Timing of Analyses

The final trial analysis for Phase I of the study will be performed after the last enrolled woman has given birth and all outcome measures have been assessed. Prior to the final analysis we will perform an interim safety analysis when ~ ½ of the study subjects have given birth. The interim safety analyses will compare the incidence rate ratio of significant adverse events (grade 3/4 & SAEs).

6.2 Analysis Populations

(ICH E3; 9.7.1, 11.4.2.5. ICH E9; 5.2)

A modified intention-to-treat approach will be used for all analyses, including all women who were randomized and received at least one dose of study drugs, and who have evaluable data on specific outcomes regardless of whether the intervention was not given for any reason.

6.2.1 Full Analysis Population

- *All subjects who were randomized and received at least one dose of study drugs*
- *All subjects with evaluable data on specific outcomes*

6.2.2 Per Protocol Population

A per protocol analysis is not planned.

6.3 Covariates and Subgroups

(ICH E3; 9.7.1, 11.4.2.1. ICH E9; 5.7)

Covariates of interest will include baseline measures of maternal age, gestational age at enrollment, gravidity, bednet ownership, socio–economic status as estimated by a household wealth index, and prevalence of malaria parasites using LAMP.

Sub–group analyses will be performed based on categories of maternal age, gravidity, and gestational age at the time study drugs were first administered.

6.4 Missing Data

(ICH E3; 9.7.1, 11.4.2.2. ICH E9;5.3. EMA Guideline on Missing Data in Confirmatory Clinical Trials)

Women in the trial who are prematurely withdrawn from the study or are not able to provide data for specific outcomes will be considered un–evaluable and will not be included in the primary trial analysis. For some outcomes missing data will be imputed based on other information (see details in Table 10 below).

6.5 Interim Analyses and Data Monitoring

(ICH E3; 9.7.1, 11.4.2.3. ICH E9; 4.1, FDA Feb 2010 “Guidance for Industry Adaptive Design Clinical Trials for Drugs and Biologics”)

6.5.1 Purpose of Interim Analyses

Over the course of the trial, we will perform an interim safety analysis in addition to a final safety analysis for a total of two sequential evaluations of study safety. The interim safety analyses will compare the incidence rate ratio of significant adverse events (grade 3/4 & SAEs).

6.5.2 Planned Schedule of Interim Analyses

The interim safety analysis for pregnant women will be performed when $\sim \frac{1}{2}$ of the study subjects have given birth. A standardized test statistic will be calculated for the adverse event incidence rate ratio. If this statistic exceeds the nominal critical value calculated using the error spending function (Table 6), then a statistically significant result will have been achieved at the time of the analysis. In that event, the sponsor will be notified and a report submitted for review by the Data Safety Monitoring Board (DSMB). For the interim safety analysis, the study team will

present information on recruitment and the results of interim safety analyses to the DSMB, which will review the data and recommend a course of action.

Table 6. Schedule of interim safety analysis and boundaries to monitor study outcome

Number of Evaluable Subjects Accrued or % of Total Accrual Time	Test Statistic		Alpha	Cumulative Alpha
	Lower Bound	Upper Bound		
N=150 or 50% of accrual time	-2.51	2.51	0.00601	0.01210
N=300 or 100% of accrual time	-1.99	1.99	0.02313	0.05000

This analysis assumes $\alpha=0.05$ (two–sided test), O’Brien–Fleming boundaries (DeMets error–spending function) and 300 trial participants. We will utilize Programs for Computing Group Sequential Boundaries Using the Lan–DeMets Method.

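### The interim safety look has two triggers about five months apart, and Table 6's bounds fit about two-thirds information, not the 50% in their row

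*SAP*

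**What the plan says.** Section 6.1: "Prior to the final analysis we will perform an interim safety analysis when ~ ½ of the study subjects have given birth". Section 6.5.2 repeats that trigger and names the statistic: about half "of the study subjects have given birth. A standardized test statistic will be calculated for the adverse event incidence rate ratio". If the statistic exceeds the critical value in Table 6, the result counts as statistically significant, the sponsor is notified and a report goes to the DSMB.

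Table 6 counts on a different scale, headed "Number of Evaluable Subjects Accrued or % of Total Accrual Time":

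- Interim row, "N=150 or 50% of accrual time": ±2.51, alpha 0.00601, cumulative alpha 0.01210.
- Final row, "N=300 or 100% of accrual time": ±1.99, alpha 0.02313, cumulative alpha 0.05000.

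The note below the table gives the basis as alpha 0.05 ("two–sided test), O’Brien–Fleming boundaries (DeMets error–spending function) and 300 trial participants"). Section 6.5.1 plans two safety evaluations in all, one interim and one final. Section 6.1 places the final analysis after the last woman has given birth and all outcomes are assessed. Section 9 counts safety from the first dose to 6 weeks post-partum.

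**The concern.** Two things do not fit together.

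First, the text and the table name different dates for one look. A woman enrolled at 12–20 weeks delivers months later, so half of accrual cannot coincide with half of deliveries. The final row has the same fault, because the end of accrual is not the time of the final analysis in section 6.1.

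Second, an error-spending bound is a function of the information fraction. For an incidence rate ratio that fraction is measured in events, or in person-time if the event rate is constant. The SAP defines no such fraction. The only fraction visible is the 50% in the row label, and the printed critical values are not those of the named function at 50%.

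At stake is the threshold for calling an interim safety difference significant. Crossing it prompts a report to a board that, under section 6.5.3, may discontinue an arm.

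**Working it through.** **1. Gap between the triggers.** Inputs: enrolment at 12–20 weeks (section 4.3.1). Delivery at 40 weeks is then 40 − 20 = 20 to 40 − 12 = 28 weeks after enrolment. Assuming a mean entry of 16 weeks and mean delivery at 39 weeks, the gap is 39 − 16 = 23 weeks, or 5.3 months. It hardly depends on how long accrual takes.

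**2. Information at each trigger.** Assumed, because the SAP gives no accrual rate: uniform accrual of 300 women; entry uniform over 12–20 weeks; first dose at week 16 if enrolled before 16 weeks, otherwise week 20; delivery at 39 weeks (SD 2); follow-up to 6 weeks post-partum; constant event rate. Information fraction = person-time accrued by the look ÷ final person-time.

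| Accrual (months) | At 150th enrolment | At 150th delivery |
|---|---|---|
| 6 | 9% | 73% |
| 9 | 15% | 69% |
| 12 | 20% | 64% |
| 18 | 30% | 59% |

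With accrual from 3 to 24 months and delivery fixed at 38 or 40 weeks, the ranges are 3–36% and 57–78%, and the two dates are 5.0–5.5 months apart.

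**3. Reproducing Table 6.** The O'Brien-Fleming-type Lan-DeMets function, two-sided 0.05, is α(t) = 4[1 − Φ(2.2414/√t)], where 2.2414 is the normal quantile with upper tail 0.05/4.

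- t = 0.50: 2.2414/0.7071 = 3.170, so α = 0.00305. First bound ±2.96, final bound ±1.97.
- t = 2/3: 2.2414/0.8165 = 2.745, so α = 0.0121. First bound ±2.51, final bound ±1.99.

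Table 6 prints cumulative 0.01210, ±2.51 and ±1.99, so its numbers belong to t ≈ 2/3. Pocock-type spending, power-family spending (exponents 1 to 3) and the classical O'Brien-Fleming bounds were tried at t = 0.50, and none gives the printed set. A three-look design at 1/3, 2/3 and 1 gives ±2.511 (0.00601, cumulative 0.0121) and ±1.993 (0.02313, cumulative 0.05) at its second and third looks, which agrees with every printed digit. Two looks at 2/3 and 1 give 0.00605 and 0.02314, which is close but not identical.

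**4. Effect on error rates.** A first look at ±2.51 spends 2[1 − Φ(2.51)] = 0.0121 wherever it falls. At 50% information the named function allows 0.00305, so the ratio is 0.0121/0.00305 ≈ 4. At 20% information it allows about 0.000001.

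Overall two-sided type I error with ±2.51 then ±1.99 held fixed (bivariate normal, correlation √t):

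| Information at interim | Overall type I error |
|---|---|
| 9% | 0.0572 |
| 20% | 0.0561 |
| 30% | 0.0550 |
| 50% | 0.0526 |
| 59% | 0.0514 |
| 64% | 0.0507 |
| 69% | 0.0499 |
| 73% | 0.0494 |

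**The case against.** The strongest reply is that little goes wrong if the look follows the text. At half delivered, 59–73% of person-time is in, the correct first bound runs from 2.70 down to 2.38, and 2.51 lies inside that range. Overall type I error is then 0.049–0.051. This stands. A reader might infer that the stated cumulative alpha fails at both triggers, or that 2.51 is badly wrong at the delivery trigger; the figures do not support either. Nor does the printed boundary assume 50% information: only the row label says so.

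The heading also says evaluable. Sections 6.2 and 6.4 tie that word to having outcome data, so 150 evaluable women could mean 150 delivered. That reading would reconcile the N = 150 part of the label, but the accrual-time alternatives in both rows would still conflict with the text.

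The plan also cites the Lan-DeMets programs, and section 6.5.5 promises adjustment for the spending function as appropriate. The method does tolerate a look at an unplanned time, provided the bounds are recomputed. But section 6.5.2 points to Table 6 for the value to apply, and nothing says on which scale to recompute it.

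Finally, this is a safety look. Crossing the bound prompts a DSMB review and stops nothing by itself, and the primary efficacy endpoint is not tested. So the point does not extend to the efficacy conclusions. The match to a three-look design suggests where the numbers came from, but the SAP does not say, and the point does not rest on it.

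**Conclusion.** The point holds in two parts. The text and Table 6 give different triggers for the same look, about five months apart. Separately, the printed critical values are wrong for the 50% in their own row: the named function with two looks gives ±2.96 then ±1.97 there, and the printed pair fits about two-thirds information.

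The effect is mainly on the interim threshold, which spends about four times the intended alpha at 50% information and far more than intended at the accrual trigger. The effect on overall type I error is small: about 0.053 at 50%, at most about 0.057 at the accrual trigger, and about 0.05 at the delivery trigger.

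The comparison of bounds at 50% and two-thirds needs only the figures in the SAP. The information fractions at the two triggers rest on the assumed accrual length, entry and delivery timing, and a constant event rate. It should be corrected before the interim look, because the table does not support the threshold at its own label.

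**What to change.** - In Table 6, remove the accrual and accrual-time labels from both rows. Label the interim row by the half-delivered trigger already in sections 6.1 and 6.5.2, and the final row by the final analysis as section 6.1 times it.
- Define the information fraction as observed grade 3/4 and serious adverse events (or person-time) divided by the projected total.
- Replace ±2.51 and ±1.99 with two-look bounds from the named function at the planned fraction, and state that fraction.
- State that both bounds will be recomputed at the fraction actually reached.

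The cost is a few lines of SAP wording and one run of the boundary program the plan already cites. No data collection or sample size changes.

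### Table 6 interim boundaries (±2.51, ±1.99) are not the Lan-DeMets O'Brien-Fleming values for one interim at 50%; the stated design gives ±2.963 and ±1.969

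*SAP*

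**What the plan says.** Section 6.1 of the SAP announces one interim: "Prior to the final analysis we will perform an interim safety analysis when" about half of the women have given birth. Section 6.5.1 counts this interim and the final safety analysis "for a total of two sequential evaluations of study safety". In section 6.5.2, Table 6 labels its two rows "N=150 or 50% of accrual time" and "N=300 or 100% of accrual time". The text under the table states alpha 0.05 ("two–sided test"), O'Brien-Fleming "boundaries (DeMets error–spending function) and 300 trial participants", and names the software as "Programs for Computing Group Sequential Boundaries Using the Lan–DeMets Method".

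Table 6 prints:

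| Look | Bounds | Alpha | Cumulative alpha |
|---|---|---|---|
| 50% | ±2.51 | 0.00601 | 0.01210 |
| 100% | ±1.99 | 0.02313 | 0.05000 |

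The monitored statistic is the standardized adverse-event incidence rate ratio. If it exceeds the tabulated value, the plan treats the result as statistically significant, notifies the sponsor and sends a report to the DSMB.

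**The concern.** Number of looks, timing, alpha, sidedness and spending function together determine the boundaries, so Table 6 can be checked directly. An O'Brien-Fleming type function spends very little alpha halfway through. A bound of ±2.51 with 0.0121 already spent is too generous for 50%.

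Table 6 is the operative rule for the interim. For an interim statistic between 2.51 and 2.96 in absolute value, the table declares significance and the named method does not. A statistician who runs the named program at 50% will get a value that disagrees with the table, and the SAP does not say which governs. Section 6.5.3 allows the DSMB to discontinue an arm after the interim. Section 6.5.5 allows reported p-values and confidence intervals to be adjusted from the specified spending function, so the discrepancy could carry into the results.

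**Working it through.** **Inputs.** Two looks (6.5.1); information times 0.5 and 1 (Table 6 row labels); two-sided alpha 0.05; O'Brien-Fleming type Lan-DeMets spending (text under Table 6).

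**Spending function.** Two-sided 0.05 is treated as two one-sided 0.025 functions:

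α(t) = 4 × [1 − Φ(z₀.₉₈₇₅ / √t)], with z₀.₉₈₇₅ = 2.2414.

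- t = 1/3: 0.00021
- t = 1/2: 2.2414/√0.5 = 3.170, upper tail 0.000763, × 4 = 0.00305
- t = 2/3: 2.2414/√(2/3) = 2.745, upper tail 0.003024, × 4 = 0.01210
- t = 1: 0.05000

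The 0.01210 in Table 6 is therefore the spend at 2/3, not at 1/2.

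**Reproducing the printed figures.** The bounds were solved by recursive numerical integration.

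| Schedule | z | One-sided nominal alpha | Cumulative two-sided alpha |
|---|---|---|---|
| 1/3, 2/3, 1 | 3.7103, 2.5114, 1.9930 | 0.00010, 0.00601, 0.02313 | 0.00021, 0.01210, 0.05000 |
| 2/3, 1 | 2.5093, 1.9929 | 0.00605, 0.02314 | 0.01210, 0.05000 |
| 1/2, 1 (stated design) | 2.9626, 1.9686 | 0.00153, 0.0245 | 0.00305, 0.05000 |

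Looks 2 and 3 of the first row match every printed digit of Table 6. The two-look schedule at 2/3 and 1 agrees on the rounded bounds but misses the nominal alphas in the last digit.

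**Other methods at 50% and 100%.** None gives ±2.51:

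- the alternative form 2 × [1 − Φ(z₀.₉₇₅/√t)]: ±2.772 and ±1.979
- classical O'Brien-Fleming: ±2.797 and ±1.977
- Pocock: ±2.178 at both looks

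**Internal check of Table 6.** At a true first look, cumulative two-sided alpha equals twice the one-sided nominal alpha. Here 2 × 0.00601 = 0.01202, but 0.01210 is printed. Rounding of 0.00601 can move the product only between 0.01201 and 0.01203. The excess fits alpha spent at an earlier look that this SAP does not have.

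**Error rate as printed.** With ±2.51 and ±1.99 at t = 0.5 and 1:

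- interim: 2 × [1 − Φ(2.51)] = 0.0121, against 0.00305; ratio 0.0121 / 0.00305 = 4.0
- overall two-sided: 0.0526 (0.0522 with the unrounded bounds 2.5116 and 1.9930 implied by the printed nominal alphas)

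If 0.0121 really were to be spent at 50%, under whatever function, the final bound would have to be ±2.016 to hold 0.05. The printed pair is therefore not a valid 0.05 design at 50% and 100%.

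**Column labels.** *Alpha* is one-sided (0.00601 = 1 − Φ(2.5116)) and *Cumulative Alpha* is two-sided, without labels. Reading a two-sided p-value against 0.00601 would mean |z| > 2.75, a third threshold.

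**The case against.** The mismatch itself is not in dispute. The serious objection is that ±2.963 need not be the right bound on the day. The statistic is a rate ratio, modelled with follow-up time as offset (section 9.3), so information follows events or person-time and not the number of deliveries. When half have delivered, the undelivered women also contribute. As an illustration on assumed figures, since the SAP gives no accrual period, take uniform accrual over 13 to 78 weeks, 20 to 28 weeks from enrolment to birth, 6 weeks postpartum and a constant event rate. The person-time fraction is then about 0.59 to 0.82. At 0.60 the bound is about ±2.67 and the printed bounds give an overall error of 0.0512; at 2/3 the figures are ±2.51 and 0.0503. This stands as a reason to recompute at the observed fraction. It does not rescue Table 6, which labels the look as 50%.

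The dropped first look is an inference. The SAP nowhere mentions a third look, and the error does not depend on this explanation.

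The consequences are also limited. The primary efficacy outcome is not tested at the interim. The DSMB sees the interim data whether or not the bound is crossed, and nothing stops automatically. The error flags harm sooner, and the final bound is slightly stricter than needed. All of this is true and bears on how much harm results, not on whether the table is right. If a more sensitive safety trigger was intended, the SAP should say so and name a function that gives it.

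Finally, the decision rule compares the statistic with the bound, so the mixed alpha columns are a labelling fault and no separate error.

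**Conclusion.** The concern holds. For the design as stated (looks at 50% and 100%, two-sided 0.05, Lan-DeMets O'Brien-Fleming spending), the bounds are ±2.963 and ±1.969, not ±2.51 and ±1.99. The printed interim bound spends 4.0 times the alpha that the named function allows, and the overall two-sided error is 0.0526 instead of 0.0500. These figures take the information fraction as 0.50, as the table itself labels it. At a higher realised fraction the discrepancy shrinks, and it nearly vanishes at 2/3. The effect on overall error is small and no automatic action follows, but the plan's only numerical interim threshold does not follow from its own method and must be corrected before it is used.

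**What to change.** Replace Table 6 with the two-look values, both alpha columns labelled two-sided:

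| Look | Bounds | Nominal alpha (two-sided) | Cumulative alpha (two-sided) |
|---|---|---|---|
| 50% | ±2.963 | 0.00305 | 0.00305 |
| 100% | ±1.969 | 0.0490 | 0.0500 |

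Add that these are planning values, that the bound will be recomputed in the same Lan-DeMets program at the information fraction observed at the interim, and how that fraction is measured (events or person-time). Keep one trigger, half of the women delivered, and delete the accrual-time alternative: women enrol at 12–20 weeks of gestation, so births lag enrolment by months and the two triggers fall at different times. If the sponsor intended a look at 2/3 or a different spending function, the row labels and the text should say so and the table be computed to match.

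The cost is one corrected table and a short addition to the text. No participants or data are added. On the planning values the interim bound becomes stricter and the final bound slightly easier (1.969 against 1.99).

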6.5.3 Scope of Adaptations

At the time of the interim analysis, the DSMB may decide to continue, stop, or modify the trial based on the interim safety analysis. This may include the discontinuation of a study arm and re–randomization or cessation of subject participation in the stopped arm.

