4.1 General Study Design and Plan

(ICH E3;9)

This will be a double-blinded randomized controlled phase III trial of 300 HIV uninfected pregnant women and the children born to them. The study interventions will be divided into two phases. In the first phase, HIV uninfected women enrolled at 12–20 weeks gestation will be randomized in equal proportions to one of three IPTp treatment arms: 1) 3 doses of SP, 2) 3 doses of DP, or 3) monthly DP. All three interventions arms will have either SP or DP placebo to ensure adequate blinding is achieved in the study. Follow-up for the pregnant women will end approximately 6 weeks after giving birth. In the second phase of the study, all children born to pregnant women enrolled in the study will be followed from birth until they reach 36 months of age. Children born to women randomized to receive 3 doses of SP during pregnancy will receive DP every 3 months between 2–24 months of age. Children born to women randomized to receive 3 doses of DP or monthly DP during pregnancy will receive either DP every 3 months or monthly DP between 2–24 months of age. To ensure adequate blinding, children who will receive DP every 3 months will be given DP placebo during the months they will not be taking DP. Children

will then be followed an additional year between 24–36 months of age following the interventions.

The details outlined in this statistical analyses plan will only focus on Phase I of the study involving pregnant women.

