6.5.4 Stopping Rules

The DSMB will determine whether to stop the study for early evidence of intervention safety problems after a thorough review of interim data. Interim reports will provide cumulative enrollment figures and cumulative adverse birth outcomes, serious adverse events (classified according to grade), sorted by study arm. Brief clinical descriptions of key events will also be provided. The PI will be responsible for immediately reporting to the funding agency any temporary or permanent suspension of the project and the reason for the suspension.

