8.1 Efficacy outcomes

Definitions and criteria used to generate estimates of all primary and secondary efficacy outcomes are presented in Table 10 below. For women with non-singleton birth (i.e. twins), dichotomous delivery outcomes at the level of the individual child/placenta will be based on whether the outcome was present in either child/placenta.

Table 10. Primary and secondary outcomes

Outcome	Category	Type of measurement	Timing of measurement	Numerator	Denominator	Missing data	Imputation
Placental malaria by histopathology	Primary outcome	Proportion	At delivery	Placental tissue samples with parasites or pigment detected	Number of placentas examined	No placental tissue sample collected	None
Placental parasitemia using microscopy	Secondary outcome	Proportion	At delivery	Placental blood samples with parasites detected by microscopy	Number of placental blood samples examined	No placental blood sample collected	None
Placental parasitemia using LAMP	Secondary outcome	Proportion	At delivery	Placental blood samples with parasites detected by LAMP	Number of placental blood samples examined	No placental blood sample collected	None
Maternal parasitemia using microscopy	Secondary outcome	Proportion	At delivery	Maternal blood samples with parasites detected by microscopy	Number of maternal blood samples examined	No maternal blood sample collected	None
Maternal parasitemia using LAMP	Secondary outcome	Proportion	At delivery	Maternal blood samples with parasites detected by LAMP	Number of maternal blood samples examined	No maternal blood sample collected	None
Cord blood parasitemia using microscopy	Secondary outcome	Proportion	At delivery	Cord blood samples with parasites detected by microscopy	Number of cord blood samples examined	No cord blood sample collected	None
Cord blood parasitemia using LAMP	Secondary outcome	Proportion	At delivery	Cord blood samples with parasites detected by LAMP	Number of cord blood samples examined	No cord blood sample collected	None
Spontaneous abortion	Secondary outcome	Proportion	At delivery	Delivery at < 28 weeks gestational age	All deliveries	Withdrawn prior to delivery	None
Stillbirth	Secondary outcome	Proportion	At delivery	Infant born deceased	Deliveries \geq 28 weeks gestational age	Withdrawn prior to delivery or < 28 weeks gestational age	None

Statistical Analysis Plan PROMOTE-II Birth Cohort 1 – Pregnant women

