Low birth weight	Secondary outcome	Proportion	At delivery	Birth weight < 2500 gm	Deliveries \geq 28 weeks gestational age	Withdrawn prior to delivery or < 28 weeks gestational age or no birth weight	Inferred if no birth weight but weight available with 7 days of birth
Preterm delivery	Secondary outcome	Proportion	At delivery	Gestational age < 37 weeks	Deliveries \geq 28 weeks gestational age	Withdrawn prior to delivery or < 28 weeks gestational age	None
Congenital malformation	Secondary outcome	Proportion	At delivery	Any congenital malformation documented on exam	Deliveries \geq 28 weeks gestational age	Withdrawn prior to delivery or < 28 weeks gestational age or infant unavailable for examination	None
Composite adverse birth outcome	Secondary outcome	Proportion	At delivery	Any of the following: spontaneous abortion, stillbirth, low birth weight, preterm delivery, or congenital malformation	All deliveries	Withdrawn prior to delivery	None
Symptomatic malaria during pregnancy	Secondary outcome	Incidence	Time at risk during pregnancy	Number of episodes of fever and positive blood smear by microscopy	Duration of observation from day following 1 st dose of study drugs to delivery or premature study withdrawal	None	None
Parasitemia during pregnancy detected by LAMP	Secondary outcome	Proportion	At the time of each routine visit	Maternal blood samples with parasites detected by LAMP	Routine visits at 20, 24, 28, 32, 36, and 40 weeks of gestational age following 1 st dose of study drugs to delivery or premature study withdrawal	Missed routine visits or samples not collected	None
Maternal anemia	Secondary outcome	Proportion	At the time of each routine visit and at delivery when phlebotomy done	Hemoglobin level < 11 g/dL	Routine visits at 20,28, 36 weeks of gestational age following 1 st dose of study drugs to delivery or premature study withdrawal	Missed routine visits or sample not collected when scheduled for phlebotomy	None

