Placental blood by LAMP	n/N (%)	n/N (%)			n/N (%)		
Maternal blood by microscopy	n/N (%)	n/N (%)			n/N (%)		
Maternal blood by LAMP	n/N (%)	n/N (%)			n/N (%)		
Cord blood by microscopy	n/N (%)	n/N (%)			n/N (%)		
Cord blood by LAMP	n/N (%)	n/N (%)			n/N (%)		
Birth outcomes							
Spontaneous abortion	n/N (%)	n/N (%)			n/N (%)		
Stillbirth ^b	n/N (%)	n/N (%)			n/N (%)		
Low birth weight ^b	n/N (%)	n/N (%)			n/N (%)		
Preterm delivery ^b	n/N (%)	n/N (%)			n/N (%)		
Congenital anomaly ^b	n/N (%)	n/N (%)			n/N (%)		
Composite adverse birth outcome	n/N (%)	n/N (%)			n/N (%)		

^a Reference group

^b Only includes those at least 28 weeks gestational age

Table 12. Longitudinal outcomes assessed during pregnancy

Outcome	Treatment arm						
	3 dose SP ^a		3 dose DP		Monthly DP		
Incidence measures	Events ^b	Events ^b	IRR (95% CI)	p-value	Events ^b	IRR (95% CI)	p-value
Symptomatic malaria	xx (x.xx)	xx (x.xx)			xx (x.xx)		
Prevalence measures	Prevalence	Prevalence	RR (95% CI)	p-value	Prevalence	RR (95% CI)	p-value
Detection of malaria parasites by LAMP							
All routine visits	n/N (%)	n/N (%)			n/N (%)		
20 weeks gestational age	n/N (%)	n/N (%)			n/N (%)		
24 weeks gestational age	n/N (%)	n/N (%)			n/N (%)		
28 weeks gestational age	n/N (%)	n/N (%)			n/N (%)		
32 weeks gestational age	n/N (%)	n/N (%)			n/N (%)		
36 weeks gestational age	n/N (%)	n/N (%)			n/N (%)		
40 weeks gestational age	n/N (%)	n/N (%)			n/N (%)		
Anemia defined as hemoglobin level < 11 g/dL							
All routine visits and delivery	n/N (%)	n/N (%)			n/N (%)		
20 weeks gestational age	n/N (%)	n/N (%)			n/N (%)		
28 weeks gestational age	n/N (%)	n/N (%)			n/N (%)		
36 weeks gestational age	n/N (%)	n/N (%)			n/N (%)		
At the time of delivery	n/N (%)	n/N (%)			n/N (%)		

^a Reference group

^b Number of events (incidence per person year at risk)

9 Safety and Tolerability Analyses

Safety and tolerability will be evaluated during the period following the 1st dose of study drug administration through the end of the observation period (6 weeks post-partum) or premature study withdrawal.

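### If the DSMB closes an arm, 6.5.3 names only re-randomisation or ending participation; carried out as leaving the study, that loses later birth and safety data and tilts what remains towards early deliveries

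*SAP*

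**What the plan says.** Section 6.5.3 is permissive. After the interim safety analysis the DSMB may continue, stop or modify the trial, and a modification may include discontinuing an arm, with re-randomisation or "cessation of subject participation in the stopped arm". Stopping study drug while observation goes on is not named.

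Other sections fix what follows if a woman leaves:

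- Section 6.4: "Women in the trial who are prematurely withdrawn from the study" count as un-evaluable and are left out of the primary analysis.
- Table 10 (Section 8.1): birth outcomes are missing if "Withdrawn prior to delivery". This includes the composite, defined as "Any of the following: spontaneous abortion, stillbirth, low birth weight, preterm delivery, or congenital malformation". The only imputation infers birth weight from a weight taken within 7 days of birth, which cannot help when the birth is not observed.
- Section 9: safety is evaluated "through the end of the observation period (6 weeks post-partum) or premature study withdrawal".

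Other sections lean towards continued observation. Section 6.2 keeps women "regardless of whether the intervention was not given for any reason", provided outcome data exist. Table 7 counts withdrawals, while Table 9 separately counts held and missed drug. Section 4.1 plans that "all children born to pregnant women enrolled in the study will be followed from birth until they reach 36 months of age".

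**The concern.** An arm would be closed because of a safety signal. Under 6.5.4, "Interim reports will provide cumulative enrollment figures and cumulative adverse birth outcomes" and serious adverse events by arm. Women exposed to the suspect regimen but not yet delivered hold the evidence that would confirm or weaken that signal: later stillbirths, malformations, low birth weights and post-partum events. If they leave, two things happen.

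- **Precision falls.** Fewer exposed women have known birth outcomes.
- **The comparison becomes selective.** Women delivered by a calendar cut-off include too many short gestations, because among women enrolled at the same time the early deliverers are counted first. The continuing arms are followed to every delivery. Table 11 would then compare unlike groups, and the closed arm would look worse on early delivery even if the regimen has no effect on gestation.

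**Working it through.** **Plan's own figure.** The SAP states no figure for this clause, so none is disputed. The base of 90 women with outcomes per arm comes from Tables 4 and 5. It is consistent with the stated power: 62% × (1 − 0.33) = 41.5%, and a two-sided 5% test of 62% against 41.5% with 90 per arm (pooled variance, no continuity correction) has power 78.9%, against the stated 80%.

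**Women undelivered at the look.** Sections 6.1 and 6.5.2 put the look at about half delivered, and Table 6 gives N=150 of 300. That is 150/3 = 50 delivered per arm, leaving at most 90 − 50 = 40. If half is taken of the 90 instead, 45 are delivered and at most 45 are left. With even accrual over A weeks (assumed) and L weeks from enrolment to delivery, the number undelivered is 90 × L/A, up to that cap. Entry at 12-20 weeks and delivery near 40 weeks give L = 20-28, midpoint 24.

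- A = 39: 90 × 24/39 = 55, so the cap of 40-45 applies.
- A = 52: 34.6 at L = 20 and 41.5 at L = 24, so about 35 up to the cap.
- A = 104: 17.3, 20.8 and 24.2 at L = 20, 24 and 28, so about 20.

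**Precision.** Upper 95% bound with zero events = 1 − 0.05^(1/n). Chance of at least one event of a 2% outcome = 1 − 0.98^n. Half-width of the 95% CI for a risk difference at 10% against 90 controls = 1.96 × √[0.09 × (1/90 + 1/n)].

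| Women with birth outcomes in the closed arm | Zero-event bound | Chance of seeing a 2% event | Half-width, points |
|---|---|---|---|
| 45 (leave; half of 90) | 6.4% | 0.60 | 10.7 |
| 50 (leave; look at 150 of 300) | 5.8% | 0.64 | 10.4 |
| 66 (45 + 20.8, followed, A = 104) | 4.4% | 0.74 | 9.5 |
| 71 (50 + 20.8, followed, A = 104) | 4.1% | 0.76 | 9.3 |
| 90 (followed, accrual complete) | 3.3% | 0.84 | 8.8 |

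**Selection with no true effect.** Simulation of 2,000,000 women per setting. Assumptions: even accrual; entry gestation uniform over 12-20 weeks; closure at the median delivery date; delivery before 28 weeks 1-3%; preterm 5-15%, either uniform over 32-37 weeks or exponential below 37 with mean 1.5 weeks; all others at 37-42 weeks. Entries are the proportion among women delivered by closure divided by the true proportion.

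| Accrual, weeks | Preterm | Before 28 weeks | Either |
|---|---|---|---|
| 39 | 1.18-1.25 | 1.82-1.85 | 1.26-1.34 |
| 52 | 1.13-1.18 | 1.62-1.66 | 1.20-1.26 |
| 78 | 1.09-1.12 | 1.42-1.45 | 1.13-1.17 |
| 104 | 1.07-1.09 | 1.31-1.33 | 1.10-1.13 |

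Example: with 2% before 28 weeks and 10% preterm among the rest, the true combined proportion is 0.02 + 0.98 × 0.10 = 11.8%. It reads 15.1-15.5% at 39 weeks and 13.1-13.2% at 104 weeks. If all women enrolled by the look are followed to delivery, it reads 11.8%.

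Sensitivity: closing at 50 of 90 delivered rather than the median lowers the preterm ratio from 1.24 to 1.21 (39 weeks) and from 1.09 to 1.07 (104 weeks). Shorter accrual raises it: with preterm births skewed towards 37 weeks over 28-37, a true 10% reads about 12% at 52 weeks of accrual and 17% at 13 weeks.

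**What is kept.** Section 9.3 models adverse events with log follow-up time as an offset, so events and person-time before closure stay in. What is lost is later safety observation, including the rest of the 6 post-partum weeks for women recently delivered: 11-38 per 100 under accrual of 52 down to 13 weeks.

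**The case against.** The strongest reply is that the clause speaks of participation in the arm, not in the study. Where the SAP means leaving the study it says withdrawn or withdrawal, and 6.5.3 uses neither word. Sections 6.2 and 4.1 and Tables 7 and 9 all fit stopping the drug and staying under observation. The sentence gives examples of what the DSMB may do, and off-drug follow-up is commonly left to a protocol or DSMB charter. Much of this stands: the drug-only reading is open, and the size of the harm rests on accrual and outcome rates that the SAP does not give.

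It does not remove the point. The phrase concerns the subject's participation, not drug administration, and it is set beside re-randomisation as the alternative. Section 6.2 says who is analysed if data exist; it does not require that the data be collected. The SAP also does not say in which arm re-randomised women are analysed.

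A reader might infer more: that the SAP orders women in a closed arm out of the study, that the arm's safety data are lost, or that the DSMB's own interim comparison is skewed. The documents support none of these. The clause is permissive, safety data before closure are kept, and at the look all arms are cut at the same date. The imbalance arises only in the final comparison.

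**Conclusion.** The point holds conditionally and is a matter for consideration, with medium confidence. It needs the DSMB to close an arm, to choose cessation over re-randomisation, and the trial team to carry that out as leaving the study. Under those conditions the SAP's own rules discard later birth and safety data for up to about 40-45 of 90 expected women per arm, or about 20 with a 24-month accrual, and leave early-delivery proportions inflated to the extent tabulated above. The direction follows from a calendar cut-off with staggered entry. The size depends on the assumed accrual length, gestation distribution and outcome rates. The protocol is not shown and may already provide for continued follow-up; if so, only the SAP wording needs to match it.

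**What to change.** Leave the drug decision to the DSMB. In 6.5.3, replace "cessation of subject participation in the stopped arm" with: *cessation of study-drug administration in the stopped arm, with scheduled visits, delivery assessments and safety follow-up continuing to 6 weeks post-partum unless consent is withdrawn*. Add that all women, including any re-randomised, are analysed in the arm of first randomisation, with safety data also shown up to the closure date. Section 6.2 needs no change. Women delivered before closure should not form a stand-alone birth-outcome analysis, because that group carries the short-gestation selection.

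The cost is a few lines of text; the visits are already scheduled and no new women are needed. There are two downsides. The closed arm's efficacy estimate by first randomisation is diluted by time off drug or on a second regimen, so the gain is in safety and birth outcomes, not placental malaria. Women off drug also keep the visit burden unless they withdraw consent. The change should be made before the interim look, since women who have left may not be recoverable.
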